9. SAFETY ANALYSES

A summary table of MedDRA-coded adverse events (AEs) will be generated, displaying the frequency and percentage of participants experiencing each AE by treatment group, system organ class (SOC), and preferred term. In addition, a comprehensive listing of all reported AEs will be provided. This listing will include onset date, verbatim term, MedDRA code, SAE/EAE classification, study day, severity grade, relationship to study drug, outcome, and duration (in days).

Deaths will be summarized separately by treatment group, as described in Section 2.2. A Kaplan–Meier survival analysis will be conducted to estimate the time-to-death distribution for each arm. Survival curves will be compared using the log-rank test. A Cox proportional hazards model will also be used to estimate the hazard ratio (HR) and 95% confidence interval (CI) for mortality between groups, adjusting for baseline creatinine clearance. In addition, subgroup analyses will be conducted stratified by baseline creatinine clearance (≥ 60 vs. < 60 mL/min).

Survival analyses will be performed across multiple time windows: through Day 28 and Day 180 (± 42 days). Participants lost to follow-up will be censored at their last known survival date.

To further explore potential differences in mortality risk across treatment phases, an interaction analysis will be conducted between treatment assignment and treatment period (during-treatment vs. post-treatment). This analysis will help assess whether the effect of treatment on mortality differs between the period of active drug administration and the post-treatment period.

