5. Duration of respiratory support (with Last-Off Approach) among Day 28 survivors, the number of days on any qualifying respiratory support (applying the last-off approach) will be summarized. Participants transferred to LTACHs will be assigned 28 days. Differences between treatment arms will be analyzed using a two-sample parametric t-test. Descriptive statistics (mean, standard deviation, median, quartiles, and range) will also be presented in summary tables.
6. Oxygenation ($\text{PaO}_2/\text{FiO}_2$ ratio) measured daily on study days 1–7 will be visualized using boxplots stratified by treatment arm.
7. ICU-free days, defined as 28 minus the number of days in the intensive care unit (ICU) during the first 28 days post-randomization.
 - Participants who do not survive through day 28 will be assigned zero ICU-free days.
 - Participants who remain in the ICU on day 27 will be assigned zero ICU-free days.
 - Participants who are transferred to LTACH facilities will be assigned zero ICU-free days.
 - Participants who withdraw from the study will be considered as having missing data.Differences in ICU-free days between treatment arms will be analyzed using a two-sample parametric t-test. Descriptive statistics (mean, standard deviation, median, quartiles, and range) will also be presented in summary tables.
8. CMV DNA detection in plasma and endotracheal aspirate (ETA) by day 28 (>0 IU/mL, >1000 IU/mL), defined as positive CMV PCR from ETA, plasma, or serum specimens.
The analysis will be conducted by the unblinded protocol statistician.
Differences in CMV DNA detection in plasma and endotracheal aspirate between treatment arms will be evaluated under the competing risk framework of Fine and Gray (10). Cumulative incidence estimates will be evaluated, and Gray's test p-value will be used to test the difference between arms accounting for death as competing risk.
 - This analysis will include death as a competing risk if it occurs on the same day of the last negative CMV test date.
 - Any CMV reactivation will be considered, even those which were below the level of quantification but greater than 0.
9. A comprehensive list of all reportable AEs of Grade 3 or higher by day 28 will be provided, including onset date, AE verbatim, MedDRA code, SAE/EAE, study day, severity grade, relationship to study drug, outcome, and duration days.

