9.11 Post-Enrollment Procedures

See the schedule of procedures for specific time points (including permissible windows) in Appendix A. Duration of participation in the study by individual patients will be 180 days.

- Blood:
 - Creatinine, Platelets, CBC w/differential - Days 4, 7, 11, 14, 18, 21, 25, 28 (all \pm 1 day); can be obtained from clinical testing results if available
 - CMV PCR (all \pm 1 day):
 - At intensified monitoring sites: Days 4, 7, 11, 14, 18, 21, 25, 28
 - At all sites: 7, 14, 21, 28 at all sites
- ETA: At intensified monitoring sites, CMV PCR, twice weekly (\pm 2 days) while intubated.
- Clinical Assessments:
 - SOFA score daily on Days 1-7, then twice weekly (Day 11, 14, 18, 21, 25, 28) through day 28 if still in the ICU
 - Vital status (collected as ICU and hospital mortality at discharge, and 180-day mortality)
 - Assessment of concomitant antiviral medications daily on Days 1-7, then twice weekly through day 28
 - Ventilator parameters and static respiratory compliance (daily if mechanically ventilated), NIV parameters, and HFNC parameters daily.
 - Net fluid balance at ICU admission and net cumulative fluid balance until ICU discharge
 - Use at any point during study (and if used, duration/number/dose) of ECMO, prone positioning, steroids, neuromuscular blockers; collected at hospital discharge
 - Occurrence of bacteremia and fungemia; collected at discharge
 - Use of antibacterials or antifungals in the event of ventilator-associated pneumonia or nosocomial pneumonia (defined as sputum, BAL or ETA culture with new pathogen associated with new antibiotic +/-48 hours from culture). Any antibacterial used to treat bacteremia or antifungal used to treat fungemia should be reported.
 - Apache III at baseline only
 - COMS survey (see Section 9.10) at Day 180 (\pm 6 weeks)
 - Bilateral versus unilateral infiltrates on chest radiograph: To be assessed as close as possible to, but not prior to, randomization. Chest radiograph at admission is acceptable if it is the only one available. If the word "bilateral" is not on the report of the chest radiograph, then the coordinator will ask the site PI to assign unilateral, bilateral, or "no infiltrates" to the patient's chest radiograph. If the word bilateral is in the report, then the coordinator will assign bilateral.
- For women of childbearing potential, a serum pregnancy test will be performed at day 7 or at the time of hospital discharge if discharged before study day 7.

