11 ADVERSE EVENT REPORTING

11.1 Reportable Adverse Events

In this trial, we will not collect data on or report every adverse event (AE) by the commonly used standard definition because critically ill patients have innumerable abnormal signs and symptoms associated with their disease that are expected. Similar to other critical care clinical trials, we will utilize a modified definition of reportable AEs.

For this trial, a reportable adverse event is defined as:

1. Any clinically important untoward medical occurrence in a patient receiving study drug or undergoing study procedures which is different from what is expected in the clinical course of a patient with acute respiratory failure/ARDS,

OR,

2. Any clinically important, untoward medical occurrence that is thought to be associated with the study drug or procedures, regardless of the “expectedness” of the event for the course of a patient with acute respiratory failure.

Expected events for patients with acute respiratory failure are clinical occurrences that are perceived by the investigator to occur with reasonable frequency in the day to day care of patients with acute respiratory failure treated in an intensive care unit with respiratory support. Examples of adverse events that are expected in the course of acute respiratory failure include transient hypoxemia, agitation, delirium, nosocomial infections, skin breakdown, and gastrointestinal bleeding. Such events, which are often the focus of prevention efforts as part of usual ICU care, will not be considered reportable adverse events unless the event is considered by the investigator to be associated with the study drug or procedures, or unexpectedly severe or frequent for an individual patient with acute respiratory failure. Examples of unexpectedly frequent adverse events would be repeated episodes of unexplained hypoxemia. This would be in contrast to an isolated episode of transient hypoxemia (e.g. SpO₂ ~85%), related to positioning or suctioning. This latter event would not be considered unexpected by nature, severity or frequency. Expected events for patients with acute respiratory failure will not be or reported in this trial.

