The research team at each site will determine if any clinical adverse experiences (while hospitalized) occur during the period from randomization through the last dose of study drug. The site research team will evaluate any changes in laboratory values and physical signs and will determine if the change is clinically important and different from what is expected in the course of patients with acute respiratory failure. If reportable adverse events occur, they will be recorded on the reportable adverse event case report form. All reportable AEs, per the modified definition above, will be graded according to CTC guidelines. The severity of each event should be classified into one of five defined categories as follows:

- Grade 1 Mild
- Grade 2 Moderate
- Grade 3 Severe
- Grade 4 Life Threatening or Disabling
- Grade 5 Death

The Safety and Protocol Adherence Review Team (SPART, see section 14.3) will also review laboratory safety and reportable adverse event data reports monthly. The DSMB will review all reportable AEs during their regularly scheduled meetings.

Note: Study drug specific laboratory events (e.g. hematologic values, renal function) will be collected as secondary safety endpoints.

Note: See additional information outlined in Section 5.4 on definitions of AEs for the purpose of post hoc analyses.

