APPENDIX F: DATA AND SAFETY MONITORING PLAN

Overview Prospective safety monitoring will be performed. Specific emphasis will be on hematotoxic effects as ganciclovir is known to be associated with these effects. The duration of treatment selected in this study is relatively short, thus we do not expect high rates of neutropenia. Relevant studies in this regard in the literature are two comparative studies of valganciclovir or ganciclovir in solid organ transplant recipients. Based on these studies, the rate of neutropenia should be approximately 2% with a 28-day course as proposed in this proposal. Most relevantly, our phase 2 RCT showed no neutropenia events. Numerous randomized trials do not show any evidence of ganciclovir causing thrombocytopenia. Mild anemia has been seen in some studies but the majority of trials did not show an association. A theoretical concern is the carcinogenicity in animal models. This effect has not been reported in humans; however, we have included a late follow-up time point to assess if there are any new diagnoses of tumors. Additional discussion of the safety profile is included in Section 3.

Safety monitoring will be by standard CTC criteria. Also, specific expected adverse effects will be tracked.

- Number and severity of reportable AEs and SAEs
- Time to neutropenia (absolute neutrophil count [ANC] < 1000, < 500 per mm³); use of G-CSF
- Time to renal insufficiency (creatinine clearance < 60, < 30 ml/min)
- Time to thrombocytopenia (platelet count < 50,000, < 20,000 per mm³)

Long-term follow-up. The final protocol will include follow-up contact after hospital discharge. This is to assess secondary efficacy endpoints. The subject will be contacted over the phone at days 28 (if discharged from the hospital before this date) and 180 to assess vital status, pregnancy, and reportable adverse events.

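### The SAP has no by-arm analysis of post-baseline neutrophils, platelets or creatinine clearance, and only lists Grade 3 or higher events, although the protocol makes these safety endpoints

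*SAP*

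**What the plan says.** Protocol section 11.1 uses a modified adverse event definition: "we will not collect data on or report every adverse event (AE) by the commonly used standard definition". Events seen as usual in acute respiratory failure are left out unless the investigator ties them to study drug or procedures, or finds them unexpectedly severe or frequent. A note in the same section handles laboratory toxicity separately: "Study drug specific laboratory events (e.g. hematologic values, renal function) will be collected as secondary safety endpoints".

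Appendix F gives the event definitions, together with G-CSF use:

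- "Time to neutropenia (absolute neutrophil count [ANC] < 1000, < 500 per" mm³)
- "Time to renal insufficiency (creatinine clearance < 60, < 30 ml/min")
- "Time to thrombocytopenia (platelet count < 50,000, < 20,000 per" mm³)

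The data are scheduled. Section 9.11 has "Creatinine, Platelets, CBC w/differential - Days 4, 7, 11, 14, 18, 21, 25, 28". Appendix A limits the draws to hospitalisation (note d) and waives creatinine for patients on renal replacement therapy (note n).

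In the SAP, section 9 states: "A summary table of MedDRA-coded adverse events (AEs) will be generated, displaying the frequency and percentage of participants experiencing each AE by treatment group", split by system organ class and preferred term. An event listing and a detailed mortality analysis follow. Section 10, item 9 states: "A comprehensive list of all reportable AEs of Grade 3 or higher by day 28 will be provided". Yet SAP section 2.2 and protocol section 5.2.1 both define that secondary endpoint as a number of patients.

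**The concern.** Protocol section 3.6.1.1.2 describes neutropenia as the main toxicity of the drug, and SAP section 4 records that enrolment was closed over safety and futility concerns. A reader of the final study report will want to know whether neutrophils or platelets fell, or renal function worsened, more often on ganciclovir. The protocol made these laboratory events endpoints in their own right, next to an adverse event definition that screens out much of what is expected in intensive care. If the SAP is followed, the endpoints drop out and the report relies on events that passed an investigator's judgement of expectedness.

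There is a second, smaller gap. The Appendix F thresholds are absolute and do not say what happens to a participant who is already past one at entry. Whoever adds the missing analysis will have to settle that.

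**Working it through.** The point concerns an absent analysis, so there is no stated figure to reproduce. The main check sets the passages side by side.

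**Step 1. Where each laboratory endpoint is analysed after baseline**

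| Protocol item | Data scheduled | SAP analysis by arm after baseline |
|---|---|---|
| ANC <1000, <500 | CBC with differential, 8 time points, days 4 to 28 | None. Section 11 compares lymphocytes and monocytes only |
| Platelets <50,000, <20,000 | Same 8 time points | None. Platelets enter only through the exploratory SOFA coagulation component, with no method given |
| Creatinine clearance <60, <30 | Creatinine, same 8 time points | None. Section 11 compares cystatin C; section 6.2 summarises renal dose adjustments by site |
| G-CSF use | Appendix F says it is tracked | None |

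SAP section 7 summarises laboratory values by arm at baseline only. SAP section 11 places its analyses in a companion document outside the final study report. SAP section 12, which lists changes from the protocol, does not mention the omission.

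**Step 2. How far the adverse event table fills the gap.** Under protocol section 11.2, ANC <500 for at least 5 days, and death with ANC <500 of any duration, are always reported. A shorter episode below 500, or an ANC between 500 and 1000, is outside that rule and depends on the section 11.1 judgement. No such rule exists for platelets or renal function.

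**Step 3. Endpoint 9.** The section 9 table counts participants per preferred term, not participants with at least one Grade 3 or higher event. Section 10, item 9 gives a listing. Neither yields the endpoint as defined.

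**Step 4. Who can meet an event at entry.** Protocol section 7.4 excludes ANC below 1000 (a white cell count above 2500 is accepted if no ANC is available). It sets no renal or platelet limit. SAP section 9 plans a baseline stratum with clearance below 60, and protocol section 8.4 provides for patients on haemodialysis. So renal and platelet events can be present at entry; an ANC event essentially cannot.

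**Step 5. What the at-risk condition does (illustration on assumed inputs).** Let *f* be the share already past the threshold and *p* the new-onset risk among the rest. Counting everyone gives *f* + (1 − *f*)*p*, so the risk difference shrinks by the factor (1 − *f*). The documents give neither *f* nor *p*. Assume new onset of 20% v 30%, 250 per arm as planned, a two-sided 5% test, and power = Φ{[|p₁ − p₂| − 1.96√(2p̄(1 − p̄)/n)] / √[(p₁(1 − p₁) + p₂(1 − p₂))/n]}:

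| Assumed *f* | Everyone counted | Ratio | Power | At risk only, n per arm | Ratio | Power |
|---|---|---|---|---|---|---|
| 20% | 36% v 44% | 1.22 | 45% | 200 | 1.50 | 64% |
| 40% | 52% v 58% | 1.12 | 27% | 150 | 1.50 | 52% |

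For example, at *f* = 40%: 0.40 + 0.60 × 0.20 = 0.52 and 0.40 + 0.60 × 0.30 = 0.58. Across *f* from 10% to 50% and assumed new-onset pairs of 10% v 18%, 20% v 30% and 30% v 42%, power runs from 15% to 69% with everyone counted and from 45% to 76% among those at risk. This shows direction and mechanism, not an estimate for this trial.

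**Step 6. Neutropenia.** Appendix F expects about 2% over 28 days: 0.02 × 250 = 5 cases. If placebo had none (assumed), exact Fisher power for 2% v 0% is 38%.

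**The case against.** Appendix F is a monitoring plan, the secondary endpoint list in protocol section 5.2.1 does not include laboratory events, and protocol section 6 gives no method for them. That explains how they were lost. But section 11.1 does call them secondary safety endpoints, and the SAP neither analyses them nor declares a change.

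A reader might infer that ganciclovir's known toxicity would be missed altogether. The documents do not support that. Prolonged severe neutropenia and death with neutropenia are always reported, any event thought to be drug-related is reportable, and reported events reach the by-arm table. Nor can one say how many renal or platelet events investigators would leave out: the section 11.1 examples of expected events name neither, although section 11.2 treats organ failures as expected for serious event reporting. Known toxicity fits neutrophils best; sections 3.6.1.1.1 and 3.6.1.3 rate the potential for thrombocytopenia and direct renal toxicity as low.

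Cystatin C, the record review of renal events in protocol section 5.4 and the SOFA components give partial renal coverage, and the companion document was not available. What is described of these analyses covers no neutrophil comparison, and platelets only through SOFA.

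Dilution is conditional. Nothing in the documents tells the analyst to count baseline cases as events, so it arises only if the Appendix F events are run without a baseline condition.

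A reader might also take the Phase 2 renal insufficiency figures in Table 3-1 as a guide to baseline prevalence. The counts reproduce: 41/72 = 56.9% and 36/84 = 42.9%, Pearson p = 0.079 against the stated .08. But they are safety outcomes by arm, not entry values, and they were lower on ganciclovir. Finally, SAP section 4 does not tie the closure to laboratory toxicity; the formal interim safety endpoint was death, which SAP section 9 analyses in detail.

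**Conclusion.** The omission stands. The protocol names the laboratory events as safety endpoints and schedules the data, but the SAP states no by-arm, post-baseline analysis of ANC, platelets or creatinine clearance and turns endpoint 9 into a list. As written, the final study report would describe these effects only through adverse events that passed the reporting filter, with guaranteed capture limited to ANC <500 lasting at least 5 days and death with ANC <500.

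No numerical size can be given. For neutrophils, about 5 expected cases in 250 make the comparison one of estimation rather than testing. For renal and platelet events an at-risk condition is needed, but the extent of any dilution is unknown because baseline prevalence is not given; the table in step 5 rests wholly on assumed rates. The 250 per arm is the planned number, and enrolment was later closed.

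**What to change.** Before the final report, add to SAP section 9, by arm:

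1. First on-study ANC <1000 and <500, platelets <50,000 and <20,000, and creatinine clearance <60 and <30, each among participants not already past that threshold at baseline. A participant entering with clearance between 30 and 60 stays at risk for the <30 event.
2. Cumulative incidence with death as a competing event, using the framework that SAP section 10, item 8 already applies to CMV detection. State how discharge is handled, since laboratory draws stop then; treating live discharge as a second competing event would give the risk of an in-hospital event.
3. New renal replacement therapy counted as a renal event for analysis, because creatinine is not required on it and the most severe cases would otherwise go unseen.
4. G-CSF use, as number and percentage.
5. In place of the section 10, item 9 listing (or alongside it), the number and percentage of participants with at least one Grade 3 or higher reportable event by day 28, with the difference and 95% confidence interval.

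Present the ANC results as estimates with intervals. Record the additions in SAP section 12, noting that the thresholds come from the protocol and the at-risk condition is new.

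The cost is SAP text and a few tables, mostly from laboratory data already scheduled. Denominators for the renal and platelet events will be smaller. Appendix A has no separate row for renal replacement therapy or G-CSF, so their data source should be confirmed.

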10. SECONDARY ENDPOINTS ANALYSES

Each secondary endpoint will be analyzed and summarized using appropriate statistical methods, and results will be presented by treatment group unless otherwise specified. Tables or figures will be used where appropriate.

1. Ventilator-Free Days (VFDs) defined as 28 days minus the total duration (in days) of invasive mechanical ventilation during the first 28 days post-randomization.
 - Participants who do not survive through Day 28 will be assigned 0 VFDs.
 - Participants who remain mechanically ventilated on Day 27 will be assigned 0 VFDs.
 - Participants transferred to long-term acute care hospitals (LTACHs) will be assigned 0 VFDs.
 - Participants who withdraw from the study will be considered as having missing data.Differences in VFDs between treatment arms will be analyzed using a two-sample parametric t-test. Descriptive statistics (mean, standard deviation, median, quartiles, and range) will also be presented in summary tables.
2. Total RSFDs without last-off approach defined as 28 minus the cumulative number of days on any form of respiratory support within 28 days of randomization, without the last-off rule applied. Participants who die before Day 28 will be assigned 0 RSFDs.

Differences in RSFDs between treatment arms will be analyzed using a two-sample parametric t-test. Descriptive statistics (mean, standard deviation, median, quartiles, and range) will also be presented in summary tables.

3. Mortality will be evaluated as a time-to-event outcome through 28 days and 180 (± 42 days). Analyses will mirror those described in Section 9, including Kaplan–Meier survival curves, log-rank tests, and Cox proportional hazards models (adjusted and stratified by baseline creatinine clearance). In addition, we will test for an interaction between treatment group and period (during- vs. post-treatment) to determine if treatment effects on mortality vary over time.
4. Duration of mechanical ventilation among participants who survive through Day 28, the total number of days on invasive mechanical ventilation will be calculated. Participants transferred to LTACHs will be assigned 28 days. Differences between treatment arms will be analyzed using a two-sample parametric t-test. Descriptive statistics (mean, standard deviation, median, quartiles, and range) will also be presented in summary tables.

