12. STATISTICAL ANALYSIS CHANGES FROM PROTOCOL

Additional analyses outlined in Section 11 will be incorporated separately in addition to the Final Study Report (FSR) statistical analysis to further investigate potential adverse outcomes associated with Ganciclovir (GCV) exposure.

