We do not expect this intervention to lead to a statistically significant difference in mortality between treatment groups. Nonetheless, mortality is a common and expected endpoint in critical care clinical trials, and it is a component of our primary outcome RSFDs. As such, we will include mortality as a secondary endpoint in this RCT. The risk of death is typically high (approximately 20%) in the patient population included in our trial. Table 6.3 shows the largest relative risk (for mortality) that we can detect in the treatment versus control group, with a sample size of 500 (including dropouts) and 80% power, and for different assumptions of overall mortality in the control arm (ranging from 10-35%).

Table 6-3. Detectable Relative Risk (Hazard Ratios) under different scenarios of control arm mortality with a two-sided test, 80% power and type I error rate of 5%.

Secondary outcome	Control arm assumption (%)	Hazard Ratio detectable*
Mortality (at 28 days)	35	0.62
	30	0.60
	25	0.56
	20	0.52
	15 [‡]	0.45
	10	0.35

* Assumes control arm mortality rate in table, power = 80%, and 0.05 alpha

‡ From GRAIL Phase 2

Based on this table, with the current sample size of 500 and assuming a control arm mortality of 20% (more realistic assumption of mortality for GRAIL Phase 3), the proposed trial will have 80% power to detect a hazard ratio of 0.52 for mortality between the Ganciclovir arm and the Placebo arm.

6.2 Statistical Analyses for Endpoints.

6.2.1 Primary Endpoint.

We will first compare baseline characteristics of the ganciclovir and placebo groups in assessment of the randomization process. Then to test the primary hypothesis that the mean difference in RSFDs between groups differs significantly from 0, we will use the 2-sample parametric t-test. The t-test is powerful and will be sufficient for our purpose, even if normality assumption for RSFDs fails to hold, as the t-test is robust to non-normality assumption for $n > 25$. However, as a confirmatory test, we will also use the 2-sample permutation t-test. The permutation test does not require any distributional assumption on the data and is valid under the much weaker assumption of exchangeability (which will be satisfied under controlled settings of a trial). As the next step, we will use the semiparametric efficient and robust method of Davidian

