2. Account for over-dispersion through the beta-binomial model: The beta-binomial distribution is a discrete probability distribution which arises when the probability of success in a fixed number of Bernoulli trials is either unknown or random. It has frequently been used in classical statistics to capture over-dispersion in binomial type distributed data [96, 97], and this will be used as another alternative approach.
3. Separate modeling of composites: In addition to the above approaches, the composite outcome will also be modeled separately for the primary analysis population and considered for assessment. Mortality will be modeled as a time to event outcome, and the Cox model will be used to evaluate whether the treatment (ganciclovir) has any effect on time to death. On the other hand, duration of time off respiratory support (total time in days not spent receiving respiratory support within the first 28 days), regardless of the mortality status, will be analyzed separately in a Generalized Linear Model to evaluate if ganciclovir increases total time off respiratory support within the first 28 days.

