9.6 First dose of study drug

Study day 1 is defined as the first calendar day on which the patient is randomized and the first dose of study drug is administered. All subsequent study days will start accordingly. At baseline, but before administration of study drug, the following procedures will need to be performed:

- Blood: Creatinine, CMV cell-mediated immunity, platelets, CMV plasma PCR, CBC w/differential, research samples.
- Endotracheal aspirate (ETA). If patient is intubated, collect an ETA specimen at baseline (\pm 1 day) and twice weekly, at the time that this procedure is routinely performed by respiratory therapy. Specimens will be labeled and stored frozen for subsequent CMV PCR analysis at the coordinating lab at Fred Hutch.
- Clinical Assessments: Apache III, SOFA, COMS survey (see Section 9.10), static respiratory compliance, ventilator parameters, assessment of select concomitant medications (steroids, immunosuppressive medications, neuromuscular blockers, and antivirals), use of ECMO and prone positioning, and bilateral vs. unilateral infiltrates on chest radiograph. See Section 9.11 for details on these assessments.

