APPENDIX G: SEPSIS CRITERIA

Sepsis is defined according to the recent Sepsis-3 consensus definition [72], as life-threatening organ dysfunction caused by a dysregulated host response to infection.

Organ dysfunction can be identified as an acute change in total SOFA score ≥ 2 points consequent to the infection.

- The baseline SOFA score can be assumed to be zero in patients not known to have preexisting organ dysfunction.
- A SOFA score ≥ 2 reflects an overall mortality risk of approximately 10% in a general hospital population with suspected infection. Even patients presenting with modest dysfunction can deteriorate further, emphasizing the seriousness of this condition and the need for prompt and appropriate intervention, if not already being instituted.

Septic shock is a subset of sepsis in which underlying circulatory and cellular/metabolic abnormalities are profound enough to substantially increase mortality.

Patients with septic shock can be identified with a clinical construct of sepsis with persisting hypotension requiring vasopressors to maintain MAP ≥ 65 mm Hg and having a serum lactate level > 2 mmol/L (18 mg/dL) despite adequate volume resuscitation. With these criteria, hospital mortality is in excess of 40%.

Abbreviations: MAP, mean arterial pressure; SOFA: Sequential [Sepsis-related] Organ Failure Assessment.

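### The only mortality hazard ratio the SAP specifies is adjusted for creatinine clearance alone, an undeclared addition to the protocol; leaving out age and APACHE III forgoes precision and correction of chance severity imbalance.

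*SAP*

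**What the plan says.** SAP section 9 plans Kaplan–Meier curves, a log-rank test and a Cox hazard ratio "for mortality between groups, adjusting for baseline creatinine clearance", with subgroups split at 60 mL/min. SAP section 10, item 3, repeats this for mortality as a secondary endpoint: "Cox proportional hazards models (adjusted and stratified by baseline creatinine clearance". Both cover Day 28 and Day 180. Neither section states a treatment-only hazard ratio.

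Protocol 6.2.2, under the alternative approaches to RSFDs, says that "the Cox model will be used to evaluate whether the treatment (ganciclovir) has any effect on time to death". It names no covariate. The adjustment covariates in protocol 5.3 and 5.3.1 include age, sex, race, comorbidity, severity of illness, APACHE III and SOFA with its components. Creatinine clearance is not listed; renal function enters only as a SOFA component.

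Age is available from the date of birth required at randomization (protocol 9.5). Severity is assessed before the first dose (protocol 9.6): "Clinical Assessments: Apache III, SOFA, COMS survey".

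SAP section 12, on changes from the protocol, says only this: "Additional analyses outlined in Section 11 will be incorporated separately" from the final study report. The creatinine adjustment and the 60 mL/min split are in sections 9 and 10, so that statement does not cover them. SAP section 4 reports the October 2024 DSMB meeting and the closure of enrolment that followed, so the SAP text postdates closure.

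**The concern.** Enrolment was closed partly on safety grounds, so the mortality hazard ratio will be read closely. The first question about any difference will be whether the arms happened to differ in severity at baseline. Randomization was stratified by site only (SAP 2.3), so nothing in the design balances severity beyond chance. Protocol Appendix G shows that severity matters for death. It puts mortality at about 10% for SOFA of at least 2 in a general hospital population, and says of septic shock: "With these criteria, hospital mortality is in excess of 40" per cent. Those figures show direction only; they give no effect size for this population.

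A model with creatinine clearance alone answers the question only in part. The covariate also appears in the SAP after closure, is not on the protocol's list and is not declared as a change. A critic could ask how it was chosen, and the documents give the sponsor no record to answer with.

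**Working it through.** **1. The plan's own power figure.** SAP 2.5 and protocol 6.1.2 (Table 6-3) state 80% power for a hazard ratio of 0.52 at 20% control mortality and two-sided 5%, "with a sample size of 500 (including dropouts) and 80% power".

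- Treatment-arm risk under proportional hazards: 1 − 0.80^0.52 = 10.96%.
- Expected deaths: 250 × (0.20 + 0.1096) = 77.4.
- Schoenfeld: Φ(|ln 0.52| × √77.4 / 2 − 1.96) = Φ(0.916) = 82.0%.
- Freedman: Φ(√77.4 × 0.48 / 1.52 − 1.96) = Φ(0.818) = 79.3%.
- Two proportions, 20% against 10.96%: 80.0%.

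With 3% loss (75.1 deaths) the three results are 80.9%, 78.1% and 78.8%. The stated figure reproduces. It is for an unadjusted comparison.

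**2. What a severity covariate would add.** The documents do not give the prognostic strength of age and APACHE III, so a range is assumed: a standardized severity score with log hazard ratio 0.3 to 1.0 per SD. A covariate correlated 0.4 with that score stands in for creatinine clearance; this correlation is also assumed. Trials were simulated with 250 per arm and arm risks of 20% and 10.96%, so that 0.52 keeps its unadjusted meaning. There were 1,500 trials per row, with Monte Carlo error of about 1 point.

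| Severity log-HR per SD (HR) | Treatment only | Plus creatinine proxy | Plus proxy and severity | Gain over proxy (points) |
|---|---|---|---|---|
| 0.3 (1.35) | 78.9% | 78.8% | 79.0% | 0.2 |
| 0.5 (1.65) | 81.5% | 81.8% | 83.1% | 1.3 |
| 0.7 (2.01) | 79.1% | 80.1% | 82.8% | 2.7 |
| 1.0 (2.72) | 80.1% | 81.3% | 88.7% | 7.4 |

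If 0.52 is instead held fixed as the severity-conditional hazard ratio, and the severity score replaces the proxy, power moves from 78.7% to 78.9%, 79.8% to 81.0%, 79.1% to 82.5% and 73.5% to 80.7%. The gains are 0.2, 1.2, 3.4 and 7.2 points. For harm, at an assumed conditional hazard ratio of 1.70, the corresponding gains are 1.1, 1.7, 3.5 and 10.7 points.

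**3. Type I error.** At a true hazard ratio of 1.0, rejection rates were 4.5% to 5.8% across all models and strengths.

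**4. Chance imbalance.** The difference between arms in mean standardized severity has SD √(2/250) = 0.0894, so its 95% limit is 1.96 × 0.0894 = 0.175 SD. The shift factor on the hazard ratio is exp(log-HR × 0.175): 1.05, 1.09, 1.13 and 1.19 for the four strengths. Adjusting for a covariate correlated 0.4 with severity leaves a residual SD of √(1 − 0.16) = 0.917, and the factors become 1.05, 1.08, 1.12 and 1.17. Under these assumptions, creatinine clearance alone removes little of the imbalance.

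**The case against.** Creatinine clearance is a sensible covariate for this drug. Protocol 3.6.1.3 and 9.12 adjust the dose by it, and Appendix F tracks clearance below 60 mL/min as a safety measure, so the 60 mL/min cut-point has a protocol source. SAP section 5 also plans multivariable models for secondary outcomes with the protocol 5.3 covariates. Mortality is a secondary outcome, and the clause says the models may include GLMs or the semiparametric method, which is not an exclusive list. The log-rank test remains and is unadjusted. All of this stands. What it does not supply is a stated Cox model for death with a fixed covariate list. The mortality subgroups by age and severity in SAP section 11 are outside the final study report.

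A reader might infer more, in four ways that the documents do not support:

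- *That planned power is lost.* With 0.52 read as the unadjusted effect it is defined for, the creatinine-only model keeps about 79% to 82%.
- *That the creatinine-only hazard ratio is biased toward 1.* At log-HR 1.0, with the conditional hazard ratio fixed at 0.52, the models averaged 0.548 (proxy) and 0.519 (severity). That gap is non-collapsibility: the two models estimate different quantities.
- *That severity imbalance invalidates the safety result.* In a randomized trial this is chance imbalance, and type I error is kept.
- *That the covariate was picked on the data.* The text postdates closure, but nothing shows how or when the choice was made.

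One further objection also stands: adding age and APACHE III now likewise fixes covariates after closure.

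**Conclusion.** The point holds as an omission and a disclosure gap. The specified analysis is valid, and the stated 80% power is intact. The SAP forgoes a nearly free gain in precision: about 0 to 3 points of power for severity log hazard ratios of 0.3 to 0.7 per SD, and about 7 points at 1.0, at the plan's own alternative. It also leaves most of any chance severity imbalance uncorrected in its one hazard ratio. At the 95% limit, that imbalance shifts the estimate by a factor of about 1.05 to 1.17 after creatinine adjustment. These sizes rest on the assumed prognostic strength and the assumed 0.4 correlation, neither of which is in the documents. The disclosure gap rests on the text alone: the creatinine adjustment and the 60 mL/min split are not planned mortality analyses in the protocol and are not declared in SAP section 12.

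**What to change.** In SAP sections 9 and 10 (item 3), for both Day 28 and Day 180:

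1. Report the treatment-only Cox hazard ratio with its 95% confidence interval beside the log-rank test.
2. Make the adjusted hazard ratio a Cox model with treatment, age, APACHE III and creatinine clearance, the last three as continuous covariates. State that this hazard ratio is conditional on severity, so it need not equal the treatment-only one.
3. Say what "Cox proportional hazards models (adjusted and stratified by baseline creatinine clearance" means: a covariate, Cox strata, or the subgroups at 60 mL/min.
4. State how creatinine clearance is set for participants on renal replacement therapy, since protocol Appendix A does not require serum creatinine for them.
5. In SAP section 12, list the creatinine adjustment, the 60 mL/min split and the added covariates, each with its timing relative to unblinding.

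The cost is a few sentences and a few lines of code; no new data are needed. The small downside is that the covariate set is fixed after enrolment closed, so the unadjusted hazard ratio must always be shown alongside.
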